7.7. UNSCHEDULED VISIT

If a subject returns to the study site on a date that is significantly outside a visit window, the following assessments will be completed:

· Record adverse events as reported by subject or observed by investigator.

8. STUDY PROCEDURES/EVALUATIONS

8.1. CLINICAL EVALUATIONS

8.1.1. QUANTITATIVE SENSORY TEST (QST)

QST will be performed in four areas: right and left superficial masseter muscle, and dorsum of the hands.

Thermal stimulation: We will use a standard clinical evaluation program designed for the Pathway system (MEDOC Israel). This program is comprised of a series of hot and cold stimuli that are delivered from a baseline temperature of 32°C bilaterally. Subjects will control the heating/cooling unit with a computer mouse and they will be instructed to tap the mouse button at the first perception of pain. Each stimulus (hot and cold) will be delivered three times in each location, and the program records the average temperature.

Algometry: We will use an algometer (Somedic, Sweden) to define pressure pain threshold and tolerance in the four regions bilaterally, and in a randomized fashion. Each area will be evaluated three times, and the ultimate pressure pain threshold and tolerance levels will be the average of the three measurements recorded.

8.1.2. SUSTAINED THERMAL PAIN THRESHOLD STRESS (STPTS) PET CHALLENGE

The STPTS challenge on the trigeminal (chin area) region was selected for various reasons, including technical elements related to receptor quantification PET methods (e.g., sustainability and stability over a sufficient amount of time so that receptor quantification can be obtained). In addition, this 20min challenge has psychophysical responses that closely mimic those reported by chronic pain patients, as opposed to briefer challenges, making it a perfect protocol to compare neuronal mechanisms of pain regulation in healthy controls and migraine patients. In fact, more than half of all migraine patients have allodynia, especially thermal as we demonstrated (Figure 9). . It is also ecologically consistent with the process under study; persistent pain (threshold) conditions are fluctuating in nature (Gorin et al., 1999). By utilizing this challenge we test the individual capacity to mobilize neurotransmitters involved in responses to the STPTS challenge. Multiple heat trials occur at constant rates (1°C/sec ascending) from a starting baseline of 32°C, the intensity of which is controlled by the individual's experience. Subjects will be instructed to tap the mouse button at the first perception of pain to return temperature to baseline level. In that manner, individuals with migraine will select their heat thermal pain threshold based on the current sensitivity, avoiding unnecessary discomfort during the experiment. Receptor binding measures require the utilization of challenges sufficiently long in duration so that a constant state can be achieved and enough data points are collected to permit quantification. If lapses of attention occur during the 20min and the patient misses the threshold, invariably he/she goes back on track for the following trial due to the brief peak of painful experience. Our

PET challenge has successfully demonstrated significant average differences in heat pain threshold levels and μ OR activation between ictal and interictal migraine phases. Most pain models do not have these characteristics because pain thresholds change over time, as the stimulus does not adapt to the progressive or faulty activation of descending anti-nociceptive mechanisms.

Figure 9. Sustained Thermal Pain Threshold Stress Challenge. Our adjustable PET apparatus, developed in house, provides a comfort contact of the probe on the patient trigeminal area for proper performance of the heat threshold trials.

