4. STUDY DESIGN

This is a phase 2, single center, three-arm, double-masked, randomized investigation of the modulation of the μ -opioid mechanisms in episodic migraine (in vivo).

The population for the study will consist of 60 patients with episodic migraine (30 for the active M1 HD-tDCS group and 30 for the placebo HD-tDCS group). In addition, we will use the data from up to 10 healthy controls who were recruited and scanned during the NINDS-K23062946 project (IRBMED #HUM00027383; [name], Principal Investigator). We will then recruit healthy volunteers to a total of 30 age- and gender-matched healthy subjects.

All subjects will be enrolled as either episodic migraine or healthy volunteers (HV; N=90); if episodic migraine (n=60), they will be randomized to one of two treatment arms: active (n=30) or sham (n=30).

Each participant will undergo the sequence of events and evaluations laid out in the Schematics of Study Design (Protocol Summary; pages vii-viii), which will take approximately 3 months. Completion of full protocol enrollment and participation is expected to take approximately 5 years.

Data will be collected either on paper or electronic CRFs (most questionnaires, screening/demographic and logistical information regarding assessments) or electronically on local systems(PET, MRI, HD-tDCS), then transferred via HIPAA-compliant methods within the UMHS system for analysis by study staff.

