11.1. STUDY HYPOTHESES

How are endogenous µ-opioid mechanisms affected in migraine patients?

Aim 1. To demonstrate that clinical and experimental pain measures in migraine patients are associated with μ OR BP_{ND} in the thalamus and other pain-related regions, even during interictal phase (non-headache phase).

We hypothesize that migraine patients will have a reduction in μ OR BP_{ND} at the baseline level. The activation of μ OR neurotransmission, calculated as reduction in μ OR BP_{ND} during a sustained thermal pain threshold stress challenge, will also be lower than in controls and both these measures will be associated with clinical and experimental pain ratings.

Feasibility: (Aim1) During the K23 NIH-NINDS award period, we evaluated *in vivo* the μ -opioid system during spontaneous episodic migraine headaches. Seven patients were scanned at interictal and ictal phases using the selective μ -opioid receptor (μ OR) radiotracer [¹¹C]carfentanil (Figure 11). In the ictal phase there was dysfunctional μ OR activation in the medial prefrontal cortex (mPFC), an area highly related to clinical pain processing. Furthermore, μ -opioid binding changes in mPFC showed moderate negative correlation with the combined extension and severity of the attacks. These results indicated for the first time the acute activation of the endogenous μ -opioid neurotransmission interacting with μ OR due to the pain of the migraine attack (DaSilva et al., 2014a).

(Aim 1.2) When challenged for sustained thermal stimulus on the trigeminal ophthalmic region (STPTS) during the ictal and interictal phases, six of those migraineurs showed ictal allodynia that was concurrent and positively correlated with μ OR activation in the midbrain, extending from red nucleus to vIPAG. These findings demonstrate for the first time *in vivo* the high μ OR activation in the migraineurs' brains in response to their allodynic experience (Figure 12 & 13)(Nascimento et al., 2014b).

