We then compared the migraineurs in the interictal phase with age and gender matched healthy controls. In our preliminary data we noticed lower μ OR BP_{ND} in pain-related brain regions, especially the thalamus (Figure 14), at baseline (no stimulus) (Aim1.1) and during thermal stimulation (STPTS) (Aim1.2). These results indicate that there is higher endogenous μ -opioid neurotransmission interacting with μ OR in migraineurs, even during the interictal phase, either by the higher occupancy or loss of μ -opioid receptors available.

Analysis: First, we will continue to examine differences in baseline µOR BP_{ND} and in the activation of µ-opioid neurotransmission in a large control sample of migraine patients to confirm our preliminary results. A mixed model of variance will be employed, accounting for age and other nuisance or potentially influencing variables (e.g., plasma levels of estradiol, proximity of attacks). Reductions in baseline µOR BP_{ND} and in the activation of u-opioid neurotransmission in migraine compared to controls should be expected. Second, we will investigate individual associations between baseline uOR BP_{ND} levels and their change during the STPTS challenge in the thalamus, other pain-related regions, and acute and chronic pain measures, as well as between µOR BP_{ND} levels and pain frequency by means of pair-wise correlation coefficients. We intend to use either Pearson's version or the Spearman's rank version of the correlation coefficient depending on whether the variables investigated follow normal distribution or not. Subsequently, we shall investigate the joint effect of pain intensity and frequency on the μORBP_{ND} by means of a multiple linear regression analysis where μOR BP_{ND} is the outcome, and the other two are used as predictor clinical variables. The linear regression analysis allows us to identify the effect of either one on µOR BP_{ND} for a fixed level of the other predictor.

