14.4. EXCLUSION OF WOMEN, MINORITIES, AND CHILDREN (SPECIAL POPULATIONS)

We will recruit and study a total of 60 patients diagnosed with episodic migraine, and 20 gender- and age-matched healthy controls, 18-65 years old (inclusive), during the 5-year course of the study. We will use the demographic and PET/MRI data from 10 additional healthy controls, who were recruited and scanned during the NINDS-K23-NS062946 project. Women and men will be recruited at a ratio of 3:1 to reflect the gender ratio prevalence of migraine in our population.

We will recruit without regard to ethnicity, and anticipate that this will reflect the racial characteristics of the general population in this region of the country. According to 2000 census data, the demographic composition of Washtenaw County is 75% White, 12% Black, 5% Asian/Pacific Islanders, 12% Hispanic or Latino (of any race), <1% American Indian/Eskimo/Aleut, and 1% Other.

We are proposing to study subjects between the ages of 18-65. Young children would be unable to participate because of blood volume limits and the utilization of ionizing radiation (PET). We draw up to 120 ml of blood in these studies, which is over the allowable guidelines for younger children. In addition, we utilize daily sessions of HD-tDCS that require careful monitoring of internal states and accurate reporting, which may be difficult to tolerate and perform for children.

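### The heat-challenge site is given in two ways, and up to 10 carried-over controls may have been challenged at a different site from the patients in the activation half of the primary outcome

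*Combined protocol and SAP*

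**What the plan says.** Section 8.1.2 describes the 20-minute heat challenge (STPTS) given during the PET scan and locates it: "The STPTS challenge on the trigeminal (chin area) region was selected for various reasons". The same section presents this as the team's existing challenge, already shown to separate ictal from interictal migraine, and mentions no change of site.

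The Aim 1 feasibility text in section 11.1 reports earlier work ("During the K23 NIH-NINDS award period, we evaluated") and gives another site for six of those patients: "When challenged for sustained thermal stimulus on the trigeminal ophthalmic region (STPTS) during the ictal and interictal phases". It continues: "We then compared the migraineurs in the interictal phase with age and gender matched healthy controls". The differences are reported at rest "and during thermal stimulation (STPTS) (Aim1.2"), the same sub-aim label that the ophthalmic challenge carries. No site is given there for the controls.

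Section 4 pools earlier controls into this trial: "we will use the data from up to 10 healthy controls who were recruited and scanned during the NINDS-K23062946 project". It adds: "We will then recruit healthy volunteers to a total of 30 age- and gender-matched healthy subjects". Section 14.4 gives the number as a flat 10, alongside 20 newly recruited: "We will use the demographic and PET/MRI data from 10 additional healthy controls".

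Section 3.3 makes the fall in binding potential during the challenge, compared between patients and controls, part of the primary outcome. The adjustment variables named in sections 11 and 11.1 include neither data source nor stimulation site.

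**The concern.** The activation contrast asks whether patients release less endogenous opioid than controls under the same heat challenge. That reading requires both groups to receive the challenge at the same place. If section 8.1.2 is followed, all 60 patients and the newly recruited controls are challenged on the chin. If the carried-over controls were challenged on the ophthalmic region, part of the control mean belongs to a stimulus that no patient receives. Any difference between the two sites in opioid response then enters the group contrast. The direction is unknown, so it could create or mask the hypothesised difference.

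If instead one of the two site descriptions is a drafting slip, there is no such bias in the controls, but the inconsistency still matters. Section 11.1 says the trial is to confirm the preliminary result, and staff working from a wrong site description would apply a different stimulus from the one behind that result. Both possibilities call for the two sections to be reconciled.

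**Working it through.** **Plan's own figure.** New plus carried-over controls: 20 + 10 = 30 (section 14.4), which matches the total of 30 in section 4. The carried-over share at planned enrolment is 10/30 = 33.3%. Because section 4 says up to 10, this is a ceiling.

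**What is known about site.**
- Patients and new controls in this trial: chin (8.1.2).
- Six K23-era migraine patients: ophthalmic region (11.1).
- K23-era healthy controls compared with those patients: site not stated.
- Carried-over controls: site not stated. Nor is it stated that they are the controls in the 11.1 comparison.

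The ophthalmic site for the carried-over controls is therefore an inference from the shared project and the shared sub-aim label.

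**Size of the shift if the sites differ.** With k carried-over controls among 30 and a site effect of D SD, the control mean moves by D × k/30. The documents give no value for D, so a range is assumed.

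| Assumed D | k = 10 | k = 5 |
|---|---|---|
| 0.25 | 0.25 × 10/30 = 0.08 SD | 0.25 × 5/30 = 0.04 SD |
| 0.50 | 0.50 × 10/30 = 0.17 SD | 0.50 × 5/30 = 0.08 SD |
| 0.75 | 0.75 × 10/30 = 0.25 SD | 0.75 × 5/30 = 0.13 SD |

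Against the planning effect size of 1.2 in section 11.2, the k = 10 shifts are 0.083/1.2 = 7% to 0.25/1.2 = 21%.

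**Effect on the test.** A two-sample t-test was simulated with 60 patients, 30 controls, equal SDs, no true group difference, two-sided 0.05 and 40,000 runs per setting. With 10 carried-over controls, the rejection rate was 5.0% at D = 0, 6.6% at 0.25, 11% at 0.5 and 20% at 0.8. With 5 carried-over controls and D = 0.5, it was about 6%.

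**Cost of using same-site controls only.**
- 60 v 30: SE factor √(1/60 + 1/30) = √0.0500 = 0.224.
- 60 v 20: SE factor √(1/60 + 1/20) = √0.0667 = 0.258.
- Ratio: 0.258/0.224 = 1.155, about 15% wider.
- If only 5 were carried over, 25 would be new: √(1/60 + 1/25) = 0.238, ratio 1.06.

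The effect detectable with 80% power at two-sided 0.05 is 0.63 SD for 60 v 30, 0.73 for 60 v 20, and 0.82 for 48 v 16 (20% dropout in both groups). All are below the 1.2 in section 11.2.

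**What is not touched.** Resting binding potential comes from the early phase of the scan, before the challenge. The active-versus-sham and pre/post contrasts are made among patients and use no controls.

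**The case against.** The strongest reply is that no confounding has been shown. The ophthalmic site is documented for six patients and for no control. Section 8.1.2 speaks of the challenge as the one already used, so one of the site words may simply be a slip. Section 8.1.2 is also the only operative description for this trial; section 11.1 is background. This stands: a reader might infer that the carried-over controls certainly had the ophthalmic stimulus, and the documents do not support that. They do not rule it out either, and nothing in the plan asks anyone to check.

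A reader might also infer that a site effect could never be separated from the group difference. That is wrong. About 20 new controls share the patients' site, so restricting to them, or fitting a source/site term, separates it.

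The stimulus is self-titrated: each subject stops the heat at first pain, so a difference in threshold between sites is partly absorbed by design. This stands for threshold. It does not remove a possible difference in opioid response.

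The size rests wholly on an assumed D, and one third is a ceiling. Both points stand.

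Finally, the covariates in the Aim 1 analysis are given as examples, and section 11.6 defers the final analysis to a Statistical Analysis Plan that is stored separately. The handling of these controls may be settled there, but that cannot be checked from this document.

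**Conclusion.** The concern holds in conditional form. Sections 8.1.2 and 11.1 give different sites for what the protocol treats as one challenge, and the site used in up to 10 of the 30 controls is unstated. If that site differs from the patients', pooling shifts the control mean in the activation contrast by up to D/3: 0.08 to 0.25 SD for an assumed D of 0.25 to 0.75, in an unknown direction. For D up to 0.5, the false-positive rate of a nominal 5% test would rise to at most about 11% in the simulated setting.

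The conclusion rests on three assumptions: that the carried-over controls were challenged at the K23-era site described in 11.1, that this site differs from the one used here, and that site affects the binding change. None is established. The issue is confined to the activation half of the primary outcome, and it does not compromise the resting comparison or the randomised comparison. It should be fixed because a bias in a primary contrast is plausible and cheap to exclude.

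**What to change.** - Reconcile section 8.1.2 with section 11.1 so that one challenge site is stated. The documents do not show which description is correct.
- Record the challenge site and the data source for every carried-over control in the analysis dataset.
- Use carried-over controls for resting binding potential. Include them in the primary activation contrast only if their challenge site matches the patients'.
- If it does not match, or cannot be established, base the primary activation contrast on the roughly 20 new controls. Fitting a source/site term is equivalent in a simple model, because the patient-versus-control estimate then rests on the new controls. Report the pooled 30 as a sensitivity analysis.

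The cost is protocol wording and two dataset fields. If the sites differ, the standard error for activation is about 15% wider (60 v 20 instead of 60 v 30). If they match, nothing is lost. No new subjects or scans are needed.

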8.1.3. MOLECULAR NEUROIMAGING MEASURE (TABLE 1)

PET Protocol	Early Phase [11C] Carfentanil 5-40min	Late Phase [11C] Carfentanil 45-90min		
Migraine Active Group	Baseline	STPTS Challenge 20min		
Migraine Sham Group	Baseline	STPTS Challenge 20min		
Healthy Control Group	Baseline	STPTS Challenge 20min		

PET Session: PET scans will be acquired with a Siemens HR+ scanner in 3-D mode (reconstructed FWHM resolution ~5.5mm in-plane/5.0mm axially) with septa retracted and scatter correction. Subjects will be positioned in the PET scanner gantry and two intravenous (antecubital) lines placed.

Receptor BP Measurements: [11C]carfentanil (CFN), a selective and specific μ -opioid receptor radioligand, is synthesized at high specific activity (> 2000 Ci/mmol) by the reaction of 11C-methyl triflate with desmethyl carfentanil as previously described. 15±1 mCi are administered to each subject with a maximum mass injection of 0.03 μ g/kg to ensure that the compound is administered in true tracer quantities, eliminating significant receptor occupancy. The percent occupancy of μ -opioid receptors at peak

regional carfentanil concentrations has been calculated at 0.2%-0.6% by utilizing the average mass of carfentanil administered and the known concentration of μ -opioid receptors in the postmortem human brain. Fifty percent of the [11C]CFN dose will be administered as a bolus, and the remainder will be administered as a continuous infusion by using a computer-controlled automated pump to achieve steady-states between specific and non-specific binding regions (5-7 minutes post-tracer administration with Logan plots, and full equilibrium conditions and Logan plots at 40 minutes post-tracer administration) for baseline (resting-state) and 20min of STPTS challenge for μ -opioid system activation analysis. Twenty-eight frames will be acquired over 90min.

Subsequently, dynamic image data for each of the receptor scans are transformed on a voxel-by-voxel basis into three sets of parametric maps, which are co-registered to each other. These are (1) a tracer transport measure (K1 ratio, proportional to cerebral blood flow; tracer transport=blood flow x tracer extraction) and receptor-related measures (non-displaceable binding potential, BP_{ND}), encompassing data from (2) 10-40 min (baselines) and (3) 45-90 post tracer administration (pain or control). These parametric images are calculated using a modified Logan graphical analysis (Logan et al., 1996) with the occipital cortex (a region devoid of μ -opioid receptors) as the reference region. The Logan plot becomes linear well within 10min after the start of radiotracer administrations with a slope proportional to the Bmax/Kd + 1 for this receptor site. Bmax/Kd is the "receptor related" measure BP_{ND}.

Blood Collection: Each subject who has agreed to participate in the genetic analysis will have the blood drawn from their arm vein during the PET session(s). Blood will be collected from an intravenous line placed in the arm opposite that used for radiotracer administration.

The blood for the genetic analysis will be collected during each subject's PET scan(s) if they have indicated their interest in participating in the genetic analysis portion of the study. At the beginning of the PET scan(s), blood will be drawn for genetic and biomarker analysis (24 mL maximum). During the PET scan(s) ~6mL of blood will be drawn at twenty minute intervals starting at time 0 minutes. The total volume of blood per PET scan will not exceed 70 mL.

MRI Acquisition: While healthy controls will only undergo one 45min MRI scan, episodic migraine patients will undergo two identical 45min MRI sessions, the week before and the week following the 10 daily HD-tDCS sessions. Before and after the MRI scan(s) participants will complete the PANAS questionnaire.

MRI scans are acquired on a 3 T scanner (General Electric, Milwaukee, WI). These images provide anatomical information for structure identification and will be utilized for the anatomical standardization to the ICBM/MNI atlas coordinate system. This will establish the linear and non-linear warping transformation matrices to be applied to the co-registered receptor binding maps. The acquisition sequence is axial T1 FAST SPGR

MR (TE = 3.4, TR = 10.5, TI = 200, flip angle 25 deg, FOV 24cm, 1.5mm thick slices, NEX = 1), acquisition matrix 256x256, 60 slices. T1-weighted MR and PET images of each subject are then co-registered to each other using a mutual information algorithm (Meyer et al., 1997). For this purpose, K1 ratio images are first aligned to the MR, and the transformation matrix applied to the co-registered BPND scans of the same image set. The MR scans are then anatomically standardized to ICBM brain atlas stereotactic coordinates by non-linear warping, and the resulting transformation matrix applied to both K1 ratio and BPND image sets (Zubieta et al., 2001, 2002; Zubieta et al., 2003b; Zubieta et al., 2003a). As an alternative approach for Aim3, 1H-MRS spectra will be collected from the ACC (3x2x3cm) based on our prior work showing Glx alterations in this region following tDCS therapy. Single-voxel point resolved spectroscopy (PRESS)(TR/TE=2000/35ms) will be performed using 'VAPOR' water suppression with 32 averages to measure Glx and NAA levels. A MEGA-PRESS experiment, which edits out the overlapping creatine peak at 3.0ppm will measure GABA levels (Mescher et al., 1998). The MEGA-PRESS experiment will use: TE=68ms (TE1=15ms/TE2=53ms); TR=1.8s; 256 transients of 2k datapoints; spectral width=2kHz; frequency selective editing pulses (14ms) applied at 1.9ppm (ON) and 7.46ppm (OFF).

For the MRI and PET sessions, patients cannot experience a migraine attack within 48 hr prior to the scan. The morning of each scan one of the researchers will call the patient to confirm absence of a migraine in the past 48 hours. If a migraine has occurred, the scan will be rescheduled. If the scans cannot be scheduled for exactly the week before and after the tDCS sessions, they will be scheduled within 2 weeks of tDCS. Also, if an unexpected problem occurs during an MRI or PET, the subject will be asked to complete an additional scan.

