3. OBJECTIVES

3.1. STUDY OBJECTIVES

Objective #1:

To demonstrate that clinical and experimental pain measures in migraine patients are associated with µOR BPND in the thalamus and other pain-related regions, even during interictal phase (non-headache phase).

Objective #2:

To determine whether 10 daily sessions of M1 HD-tDCS have modulatory effect on clinical and experimental pain measures in migraine patients.

Objective #3:

To investigate whether repetitive active M1 modulation induces/reverts thalamic µOR BPND, and whether those changes are associated with clinical and experimental pain measures in migraine patients.

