5. STUDY ENROLLMENT AND WITHDRAWAL

5.1. SUBJECT INCLUSION CRITERIA

In order to be eligible to participate in this study, an individual must meet all of the following criteria:

- Provide signed and dated informed consent form
- Willing to comply with all study procedures and be available for the duration of the study
- Male or female, aged 18 to 65, inclusive, and
- Meet criteria for an "episodic migraine" patient:
 - Episodic migraine (ICHD-3-beta) with at least one attack per month and less than 15 attacks per month
 - Migraine for at least 6 months
 - No intake of opiate medication for the past six months
 - No overuse of analgesic medication, defined as regular intake on
 ≥15 days per month for more than 3 months
 - Willing to limit the introduction of new treatments for headache management

OR

- Meet criteria as a Healthy Volunteer:
 - Without medication overuse
 - Without self-reported history of systemic disorders or other pain disorders, including migraine.

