5.2. SUBJECT EXCLUSION CRITERIA

An individual who meets any of the following criteria will be excluded from participation in this study:

- Presence of any other systemic or chronic pain disorder
- History or current evidence of a psychotic disorder (e.g. schizophrenia) or substance abuse; bipolar or severe major depression, as evidenced by Beck Depression score of ≥ 20*
- Prior use of tDCS
- Ongoing, unresolved disability litigation
- History of neurological disorder (e.g. epilepsy, stroke, neuropathy, neuropathic pain)
- Current use of opioid pain medications
- Allergic response to study radiotracers or chemically-related drugs
- Excluded by MRI Center or PET Center safety screening checklist (as administered by study staff)
- Female participants who are pregnant, nursing, or planning a pregnancy, or who are of childbearing potential and are not using a reliable means of contraception during the baseline and study periods (negative urine pregnancy test must be available before any procedures are initiated)
- Treatment with an investigational drug, device or other intervention within 30 days of study enrollment (Screening Visit).
- Anything that would place the individual at increased risk or preclude the individual's full compliance with or completion of the study (eg, medical condition, laboratory finding, physical exam finding, logistical complication).

^{*} The Beck Depression Inventory will be graded by study staff at the time of completion. Individuals with a score of ≥ 30 will be provided with a pamphlet from the Michigan Depression Center that contains information and contacts regarding depression. In addition, those individuals who respond to question #9 with answers #2 or #3, will be provided with a flyer from the Department of Health and Human Services National Suicide Prevention Lifeline (800 number and website).

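### The interictal scan rule screens only for migraine in the past 48 hours, so a scan with another headache, or one starting after the morning call, still counts as non-headache

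*Combined protocol and SAP*

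**What the plan says.** Objective 1 (section 3.1) is to show that pain measures in migraine are associated with µ-opioid receptor binding "even during interictal phase (non-headache phase"). The protocol thus equates interictal with free of headache.

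Section 8.1.3 turns this into a scan rule: "For the MRI and PET sessions, patients cannot experience a migraine attack within 48 hr prior to the scan". It is checked once: "The morning of each scan one of the researchers will call the patient to confirm absence of a migraine in the past 48 hours". The consequence is "If a migraine has occurred, the scan will be rescheduled". No condition covers other kinds of headache, headache at tracer injection, or attacks after the scan.

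Related provisions:
- Section 5.1 admits patients "with at least one attack per month and less than 15 attacks per month".
- Section 5.2 excludes "Presence of any other systemic or chronic pain disorder". This does not name occasional non-migraine headache.
- Section 11.1 gives examples of covariates for the Aim 1 mixed model: "e.g., plasma levels of estradiol, proximity of attacks". Proximity is not defined, and the text does not say whether it refers to the last or the next attack. The Aim 3 examples do not include it.
- Appendix A marks the visual analog pain scale (VAS), GeoPain and the short-form McGill at both PET/MRI visits. The schedule's footnote on timing places ratings before and after scans. No rule uses them to flag, exclude or reschedule a scan.

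**The concern.** The state claimed and the state checked are different. Two kinds of scan can be labelled interictal although headache is present: one with a non-migraine headache, and one where a headache begins between the morning call and the scan. If the late headache is a migraine, the written rule is breached, but the stated check would not find it.

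The protocol itself says that headache state moves the outcome. Section 2.2 reports lower BP_ND during attacks, including in the thalamus, and section 11.1 reports ictal binding changes related to the extent and severity of the attack. Aim 1 expects lower baseline BP_ND in patients than in controls. Headache-present scans could therefore push the baseline comparison towards the hypothesis. This argument on direction covers baseline BP_ND only. For the heat-challenge response, section 11.1 describes high activation with ictal allodynia, which would not obviously favour the lower activation that is hypothesised.

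A second, weaker issue concerns the within-migraine analyses. Section 11.1 correlates BP_ND with pain frequency and then regresses it on intensity and frequency. Patients with frequent attacks will more often be scanned shortly before one. If binding were already altered at that point, nearness to an attack could be mistaken for a stable trait linked to frequency. Without a date for the next attack, this cannot be examined.

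**Working it through.** **1. Claim against rule.** The documents give no figure to reproduce, so the first step is a comparison of wording.

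| Situation at scan | Free of headache (section 3.1)? | Passes the check in section 8.1.3? |
|---|---|---|
| Migraine in past 48 h, reported at the call | Not necessarily | No, rescheduled |
| Non-migraine headache present | No | Yes |
| Headache starting after the call, before or during the scan | No | Yes, the check has already been made |
| No headache, attack begins hours later | Yes | Yes |

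The second and third rows are the mismatch. The fourth row is labelled correctly. The documents give no rate for non-migraine headache, so I put no number on row two.

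**2. Nearness to the next attack.** The frequencies lie in the eligible range of section 5.1 (1 to under 15 a month). I assume attacks follow a Poisson process with m attacks per 30 days and that scans are timed independently of coming attacks. The chance that an attack starts within h hours after a scan is

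P = 1 − exp(−m·h / (24·30)).

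For h = 48 the exponent is −m/15. At m = 1, 1 − exp(−0.067) = 6.4%. At m = 14, 1 − exp(−0.933) = 60.7%.

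| Attacks a month | Within 24 h | Within 48 h |
|---|---|---|
| 1 | 3.3% | 6.4% |
| 4 | 12.5% | 23.4% |
| 8 | 23.4% | 41.3% |
| 14 | 37.3% | 60.7% |

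The ratio at 48 h is 60.7/6.4, about 9.5. A Poisson process has no memory, so the look-back rule does not lower these figures.

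**3. Sensitivity to the model.** A renewal simulation used attack durations of 4 h or 24 h and gamma-distributed gaps of shape 1 (random) or 3 (more regular), all assumed. The 48 h shares were 6.5–7.4% at 1 a month, 24–37% at 4, 43–75% at 8 and 64–99% at 14. The rise with frequency held in every variant. The top of the last range is barely attainable: with 24 h attacks and regular gaps at 14 a month, only 2.5% of time would pass the rule at all.

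**4. Can the next attack be dated?** Appendix A has no such field. Ratings at the HD-tDCS sessions give some forward information after scan 1, but they do not record the onset of attacks. Scan 1 may be as early as Day −21, so recall at Day 0 could span three weeks. Appendix A places Week 1 in the same Day 16 ± 2 window as scan 2, and section 7.4 lets the visits be combined. (Section 7.4 prints Day 37 ± 2 for Week 1, which should be reconciled with Appendix A.) If they coincide, the next contact is Month 1, nominally 37 − 16 = 21 days later.

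**The case against.** The strongest reply is that a scan hours before an attack, with no headache present, meets the protocol's own definition of interictal. A reader might infer from the one-sided window that such scans are mislabelled. The documents do not support that. They report altered BP_ND during attacks, not in the hours before one or during other headaches. Nor do the 6–61% figures measure bias. They count scans that precede an attack, and the upper figure applies only near the eligibility ceiling, with no distribution of attack frequency given. All of this stands, and it reduces the pre-attack issue to an unexcluded confounder of the within-migraine analyses. The group contrast with controls does not rest on it.

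The plan also has partial safeguards: proximity is a named covariate, pain is rated at scan visits, and section 11.6 leaves the final analysis to a separate Statistical Analysis Plan. A reader might infer that proximity could be computed only backwards. That is too strong, given the ratings at the stimulation sessions. Still, proximity is only an undefined example, it is not named for the frequency correlation or regression, and nothing in the text provided acts on the pain ratings.

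Finally, remedies can do harm. Excluding or adjusting Aim 3 scans for attacks after scan 2 would condition on an event after randomisation that active stimulation is meant to reduce. Time to the nearest attack is also largely a function of frequency, so entering both invites collinearity. Both objections are accepted and shape the fix.

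**Conclusion.** The mismatch between the headache-free claim and a migraine-only, backward-looking check holds on the wording alone. Its effect on Aim 1 is possible rather than shown. The protocol's findings during attacks point towards the baseline hypothesis, but applying them to a non-migraine headache is an assumption, and the number of affected scans is unknown.

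The rise in nearness to the next attack with frequency, about tenfold or more from 1 to 14 attacks a month, is robust across the models tried. It rests on assumed attack processes, and it matters only if binding changes before onset, which the documents do not show. It is not evidence that the BP_ND–frequency association would be biased. The gradient is shown for pre-attack scans only, not for other headaches.

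This is a cheap improvement that protects the interictal claim. It is not a flaw that invalidates the design.

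**What to change.** 1. In section 8.1.3, have the morning call ask about headache of any type as well as migraine in the past 48 hours, and confirm before tracer injection that no headache is present.
2. Flag any scan with pre-scan head pain above zero on the VAS or GeoPain already collected.
3. Add one case report form field for the date and time of the first attack after each scan, completed at contacts already scheduled: the HD-tDCS sessions after scan 1, and Week 1 after scan 2, or Month 1 if Week 1 coincides with the scan.
4. Repeat the Aim 1 baseline analyses without flagged scans and, separately, without scans followed by an attack within 48 hours of scan 1. Label both as sensitivity analyses.
5. Define the proximity covariate. Report migraine-only models with time to the nearest attack as a sensitivity check only.
6. For Aim 3, describe attack timing after scan 2 by arm. Do not exclude or adjust on it.

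The cost is a changed script line, a check at injection, one form field and some extra analyses, with no new visit. The downsides are a few more rescheduled scans, recall error in attack dates, and fewer scans in the sensitivity analyses, lost mostly from high-frequency patients (about 61% at 14 a month under the Poisson model), which narrows the range of the frequency predictor.
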